# 12.4 Univariable CoR: Supportive Exploratory Flexible Parametric Risk Modeling

For each of the five non-baseline subtracted Day 57 antibody markers, flexible nonlinear modeling of outcome risk studied as a dichotomous outcome Y will be conducted, as exploratory supportive analyses. Again, the analyses adjust for the same baseline factors X as used in the Cox model CoR analyses.

The nonlinear relationship between the logit of risk and markers will be modeled using two-phase polynomial regression models (Son and Fong, 2020; Fong et al., 2017), e.g., hinge model, or three-phase segmented models (Chen, 2020). The mean function of a  $q^{th}$  order two-phase polynomial regression model can be expressed as follows:

$$\eta(s,X) = \alpha_1 + \alpha_2^X z + \beta_{1,-}(s-e)_- + \beta_{1,+}(s-e)_+ + \beta_{2,-}(s-e)_-^2 + \beta_{2,+}(s-e)_+^2 + \cdots + \beta_{q,-}(s-e)_-^q + \beta_{q,+}(s-e)_+^q,$$

where X is the baseline covariate vector, s is a fixed value of the immunologic marker of interest, e is the threshold parameter,  $(s - e)_+ = s - e$  if s > e and 0 otherwise, and  $(s - e)_- = 0$  if s > e and s - e otherwise.

In addition, a generalized additive model with degree of smoothing estimated by cross-validation is employed (Wood, 2017). Two-phase sampling designs are accounted for through inverse probability weighting and confidence intervals are obtained through the same bootstrap scheme as the Cox proportional hazard model bootstrap inference.

## 12.4.1 [With Day 29 markers]

For CoR analyses of Day 29 markers, the same analyses are done, except using the Day 29 visit date as the time origin and counting events starting 7 days after the Day 29 visit.

#### 12.4.2 P-values and Multiple hypothesis testing adjustment for CoR analysis

In general, p-values are only reported from pre-specified and automated (press-button) analyses. For the CoR analyses, p-values are reported for the univariable Cox regression analyses of the five specified Day 57 antibody marker variables. Two-sided p-values for hypothesis testing of a Day 57 marker CoR are calculated both for the Cox regression of quantitative markers (two-sided Wald tests), and for the Cox regression of markers binned into tertiles (two-sided Generalized Wald tests). Therefore a total of ten 2-sided p-values for CoRs are calculated.

It is not completely clear whether to perform multiple hypothesis testing adjustment, given the expectation that the correlations among the markers are high, and possibly very high, meaning that multiplicity correction could incur a relatively high cost on the false negative error rate.

However, given that robust evidence supporting an antibody marker as a CoR will be required for qualifying a marker, we will conduct multiplicity adjustment for CoR analysis, as the ability to make an inference that a marker passed pre-specified multiplicity adjusted criteria should aid an overall evidence package for establishing a validated or non-validated surrogate endpoint. Therefore, multiplicity adjustment is performed across the ten 2-sided p-values.

A permutation-based method (Westfall et al., 1993) will be used for both family-wise error rate (Holm-Bonferroni) and false-discovery rate (q-values; Benjamini-Hochberg) correction.  $10^4$  replicates of the data under the null hypotheses will be created by randomly resampling the immunologic biomarkers with replacement. For each Cox regression CoR analysis the unadjusted p-value, the FWER-adjusted p-value, and the q-value is reported for whether there is a covariate-adjusted association, where all p-values and q-values are 2-sided. The FWER-adjusted p-values and q-values are computed pooling over both the quantitative marker and tertilized marker CoR analyses. As a guideline for interpreting CoR findings, markers with FWER-adjusted p-value  $\leq 0.05$  are flagged as having statistical evidence for being a CoR. Additionally, markers with unadjusted p-value  $\leq 0.05$  and q-value  $\leq 0.10$  are flagged as having a hypothesis generated for being a CoR.

As described in this SAP, the FWER adjustment is done for all advanced Day 57 markers among bAb Spike, bAb RBD, PsV nAb ID50, PsV nAb cID80, and WT LV MN50. If the antibody data set available for correlates analysis does not yet contain the WT LV MN50 data (due to a longer time horizon on performing the assay), then the multiplicity adjustment will be performed for the available 4 markers.

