#### 4.3 Synthesis of the Phase 3 Correlates Analyses for Decisions

Establishment of an immunologic biomarker for approval/bridging applications is generally not based on pre-fabricated criteria nor a single type of correlates analysis. Therefore, the goal of the correlates analysis is to generate evidence about correlates from many perspectives, and to synthesize the evidence to support certain decisions. Consequently, we believe there is value in assessing all of the types of correlates presented in Table 1 in each trial, given that the analyses address distinct questions. Obtaining a set of results from multiple distinct approaches that provide complementary and coherent support may increase the rigor and robustness of an evidence package supporting potential use of an antibody marker as a validated surrogate (for traditional approval) or as a non-validated surrogate (for accelerated approval) (Fleming and Powers, 2012); these uses of a biomarker are summarized below. However, the assumptions needed for valid inferences are somewhat different across the methods, and some of these assumptions have testable implications; therefore examination of the assumptions may lead to favoring some methods over others, and affect the synthesis and interpretation of results, and moreover if diagnostics support that some necessary assumptions are infeasible then certain analyses will be canceled, as described below.

Section 16 summarizes the approach to use and interpretation of the set of multiple correlates of protection methods. Furthermore, depending on the number of study endpoints in the vaccine and placebo arms at the time a trial delivers primary results, some of the Day 57 marker correlates types defined in Table 1 will be evaluable at the first correlates analyses, whereas others will not be evaluable until additional evaluable vaccine breakthrough endpoints have been observed.

As detailed in Table 4, some CoR analyses are done after there are at least 25 evaluable vaccine breakthrough cases, which is considered to be a minimal number to achieve worthwhile precision. On the other hand, the most non-parametric/flexible CoR analyses require more cases, as do the CoP analyses in general, given the need to adjust for all potential confounders in order to fully identify the causal effects parameters of interest and the greater challenge in estimation (compared to CoR analysis) posed by the need to deal with missing potential outcomes.

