- 4. Tabular reporting of the hazard ratio for the Middle and Upper categories of the categorical Day 57 antibody marker vs. the Lower category, with 95% confidence interval and 2-sided p-value, as well as a global generalized Wald two-sided p-value for whether the hazard rate of the endpoint varies across the three categories. The table includes the attack rate (with no. of cases / no. at risk) through  $t_F$  for each of the three vaccine marker subgroups and for the placebo arm.
- 5. Report point and 95% CI estimates for the hazard ratio per 10-fold change in the Day 57 antibody marker, for the entire per-protocol baseline negative vaccine cohort and for each of the baseline demographic strata subgroups defined in Table 6 (reported via forest plotting).
- 6. Westfall-Young (1997) q-values and FWER-adjusted p-values for the generalized Wald tests are included in the table.

Grambsch and Therneau (1994) tests are applied to test the veracity of the proportional hazards assumption. This testing is done to aid interpretation of results, but not as a gateway to trigger the fitting of a more flexible version

of the Cox model, as we seek to avoid computing new confidence intervals and p-values contingent on goodness-of-fit-testing, as they would not have their correct interpretations. Other correlates of risk methods explicitly model risk flexibly as a function of the marker.

The bootstrap is used to calculate 95% pointwise CIs for  $risk_1(t_F|s)$  in s. The 2-sided Wald p-value for testing the regression coefficient of the marker in the Cox model provides a valid test of the null hypothesis  $H_0: risk_1(t_F|s) = risk_1(t_F)$  for all s, and is reported.

In addition, the same Cox model analysis will be used to estimate the alternative marginalized conditional risk parameter defined by  $risk_1(t|S \ge s)$  where  $risk_1(t|S \ge s) = E_X[P(T \le t|S \ge s, X, A = 1)]$ , which can be estimated by

$$\widehat{risk}_1(t|S \ge s) = \frac{1}{n} \sum_{i=1}^n (1 - \hat{S}_1(t|S \ge s, X_i)).$$

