To specify  $B(s_1, s_2)$ , we note that it should have greater magnitude for a greater distance of  $s_1$  from  $s_2$ , as determined by specifying  $RR_{UD}(s_1, s_2)$  and  $RR_{EU}(s_1, s_2)$  increasing with  $s_2 - s_1$  (for  $s_1 \leq s_2$ ). We consider one specific approach, which sets  $RR_{UD}(s_1, s_2) = RR_{EU}(s_1, s_2)$  to the common value  $RR_U(s_1, s_2)$  that is specified log-linearly:  $\log RR_U(s_1, s_2) = \gamma(s_2 - s_1)$  for  $s_1 \leq s_2$ . Then, for a user-selected pair of values  $s_1 = s_1^{fix}$  and  $s_2 = s_2^{fix}$  with  $s_1^{fix} < s_2^{fix}$ , we set a sensitivity parameter  $RR_U(s_1^{fix}, s_2^{fix})$  to some value above one. It follows that

$$\log RR_U(s_1, s_2) = \left(\frac{s_2 - s_1}{s_2^{fix} - s_1^{fix}}\right) \log RR_U(s_1^{fix}, s_2^{fix}), \quad s_1 \le s_2.$$

We anchor the sieve analysis by setting  $s_1 = s_1^{fix}$  at the 15th percentile of the

Day 57 antibody marker and  $s_2 = s_2^{fix}$  at the 85th percentile of the Day 57 antibody marker.

The sensitivity analysis is done for each of the two Cox model CoR analyses described in Section 12.3.3, first for tertiles of the Day 57 marker and second for the quantitative marker. For the former, E-values are reported for both the point estimate and the upper 95% confidence limit for  $RR_C(0, 1)$ , where category 1 is the upper tertile, category 0 is the lower tertile, and the intermediate middle tertile subgroup of vaccine recipients is excluded from the analysis. In addition, setting  $RR_{UD}(0,1) = RR_{EU}(0,1) = 2$ , such that B(0,1) = 4/3, we report conservative estimation and inference on the causal risk ratio  $RR_C(0,1)$  and equivalently on the ratio of controlled vaccine efficacy curves (1 - CVE(1))/(1 - CVE(0)).

Next we repeat the analysis treating S as a quantitative variable, where  $P(T \leq t | S = s, X, A = 1)$  is again estimated by two-phase Cox partial likelihood regression and now  $RR_M(s_1, s_2)$  is the marginalized risk ratio between  $s_1$  and  $s_2$ . We will plot point and 95% confidence interval estimates of the observed marginalized risk and controlled risk curves, for the latter using the sensitivity analysis described in Section 15.1.1.

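### At 25 cases the tertile Wald test gives a conservative unadjusted p-value, and a tertile with no cases yields p = 0 and a spuriously narrow hazard-ratio interval

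*Combined protocol and SAP*

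**What the plan says.** Section 12.4.2 of the SAP sets out ten p-values: five markers, each analysed as a quantitative variable and "for the Cox regression of markers binned into tertiles (two-sided Generalized Wald tests". Section 12.3.3 (output items 3 to 6) describes the output. Item 4 reads "Tabular reporting of the hazard ratio for the Middle and Upper categories of the categorical Day 57 antibody marker vs. the Lower category", each ratio with a 95% interval and p-value, plus a "global generalized Wald two-sided p-value for whether the hazard rate of the endpoint varies across the three categories". The fit uses the survey package with a two-phase design-based variance. Section 12.7.3 names the robust variance for the Wald test of the multivariable models, which are fitted in the same way.

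On timing, Section 4.3 states that "some CoR analyses are done after there are at least 25 evaluable vaccine breakthrough cases". Tables 4 and 10 put the tertile Cox analysis at 25, and Table 10 lists no other requirement. The plan gives no minimum per tertile and no rule for an empty one. Section 12.3.3 does limit its risk curve for subgroups above a threshold to the range supported by at least 5 cases, so sparse data were considered there.

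Section 12.4.2 then says that "multiplicity adjustment is performed across the ten 2-sided p-values", using 10^4 resampled null data sets. An FWER-adjusted p-value of 0.05 or less marks statistical evidence. Markers with an unadjusted p-value of 0.05 or less and a q-value of 0.10 or less "are flagged as having a hypothesis generated for being a CoR". Section 15.1.1 adds that for the tertile comparison "E-values are reported for both the point estimate and the upper 95% confidence limit".

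**The concern.** Twenty-five cases over three tertiles is about 8 per tertile when the marker has no effect, and fewer in the upper tertile when it is protective. A Wald test on log hazard ratios behaves poorly at such counts. The estimated variance of the upper-tertile coefficient grows as that tertile empties, which holds the statistic down. When the tertile is completely empty the coefficient diverges, but a robust variance does not follow it, so the statistic explodes.

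Two outputs are at stake: the unadjusted tertile p-value, which is reported and enters the hypothesis-generating flag, and the hazard ratio, interval and p-value printed for a sparse tertile. The resampling of Section 12.4.2 is described for FWER-adjusted p-values and q-values. It does not touch the pairwise hazard ratios and intervals.

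**Working it through.** The SAP states no size, power or effect size for this test, so there is no figure of its own to reproduce beyond 5 markers × 2 codings = 10 p-values, which is correct.

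**Inputs.** From the documents: 25 cases (Tables 4 and 10); 6 strata × 150 = 900 baseline-negative vaccine recipients in the subcohort (Table 5), taken as 300 non-cases per tertile; nominal level 0.05, two-sided. Assumed: the risk ratios over tertiles and, for the Cox simulation, 14,000 vaccine recipients and the covariate effects.

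**1. Size.** With d_j cases in tertile j, let w_j = 1/(1/d_j + 1/300) and m = Σw_j log d_j / Σw_j. The Wald statistic is W = Σw_j(log d_j − m)², compared with 5.99 (chi-square, 2 df). For 15/9/1 cases the weights are 14.29, 8.74 and 0.997, and m = 2.410. So W = 1.27 + 0.40 + 5.79 = 7.45 and p = 0.024. The score statistic Σ(d_j − 25/3)²/(25/3) is 11.84, with p = 0.0027.

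Exact enumeration of all splits of 25 cases under the null gives a Wald size of 2.7% (3.5% at 35 cases, 3.6% at 50). A simulated weighted case-cohort Cox model with covariates and design-based variance gives 3.0% (3.7% at 35, 4.2% at 50).

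**2. Power of the tertile test alone, 25 cases, nominal 5%.** 'Own null' means that the Wald statistic is referred to its own null distribution.

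| Risk ratios | Enumeration: Wald / own null | Weighted Cox: Wald / own null / score |
|---|---|---|
| 1:0.5:0.25 | 57.8 / 64.0% | 49 / 58 / 62% |
| 1:0.6:0.36 | 32.5 / 38.5% | 27 / 35 / 39% |
| 1:0.7:0.49 | 15.7 / 20.0% | 13 / 19 / 21% |
| 1:0.4:0.16 | 83.5 / 87.2% | 72 / 79 / 83% |
| 1:1:0.3 | 35.4 / 46.1% | 22 / 35 / 44% |

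For the four graded rows the loss runs from about 4 points (87.2 − 83.5) to 13 (62 − 49). For the threshold row it is 11 to 22. The score comparison is somewhat generous, because that test rejected 5.8% of null data sets in the weighted simulation.

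**3. Empty tertile.** The chance that the upper tertile is empty is (1 − q)^25, where q is its share of the risk:
- 1:0.5:0.25: q = 0.25/1.75 = 0.143, chance 2%
- 1:0.4:0.16: q = 0.16/1.56 = 0.103, chance 7%
- 1:0.4:0.1: q = 0.1/1.5 = 0.067, chance 18%

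Under the null the chance that any tertile is empty is 3 × (2/3)^25 = 0.00012.

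With 15/10/0 cases a weighted Cox fit stops at log HR −18.9 with robust SE 0.27. The interval is exp(−18.9 ± 1.96 × 0.27), that is 3.7e-9 to 1.1e-8, with p = 0. The exact coefficient depends on when iteration stops. The SE is little more than the lower tertile's own contribution, √(1/15 + 1/300) = 0.26, because the empty tertile adds almost nothing to a sandwich variance. The score test on the same counts gives p = 0.0009. Referring the Wald statistic to its null distribution gives p = 0.0001.

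**4. E-value.** With fixed cut-points, every bootstrap replicate of an empty upper tertile has zero risk, so the upper limit is 0 and the Section 15.1.1 formula, (1 + √(1 − UL))/UL, is infinite. For comparison, an exact conditional limit for 16/9/0 cases is (1 − 0.025^(1/16))/0.025^(1/16) = 0.206/0.794 = 0.26, and the E-value is (1 + √0.74)/0.26 = 7.2. That split has 25 cases and only illustrates the formula; the E-value analysis needs 50. At 50 cases the chance of an empty upper tertile is 0.04% for 1:0.5:0.25, 3% for 1:0.4:0.1 and 15% for 1:0.3:0.05.

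**The case against.** The strongest reply is that the decision rule is not the raw tertile p-value. Section 12.4.2 pools quantitative and tertile tests and calibrates the adjusted values by resampling. In the enumeration, resampling the Wald statistic brings its size to 4.1% (the counts are discrete) and its power at 1:0.5:0.25 from 58% to 64%.

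A simulation of the pooled min-P rule (25 cases, five markers correlated 0.8, no covariates, Monte Carlo error about 2 points) gave marker-level FWER flag rates, Wald versus score for the tertile tests, of 50% vs 48% at 1:0.5:0.25, 77% vs 76% at 1:0.4:0.16 and 53% vs 58% at 1:0.3:0.3. The quantitative test compensates. On the unadjusted p-value part of the hypothesis-generating flag, counting either coding, the gap was 0 to 2 points. This reply stands for the flags. It does not stand for the tertile row read alone. A second simulation (correlation 0.85) put the power of that row after min-P at 33% with the Wald test and 41% with the Wald test calibrated to its own null, at 1:0.5:0.25. For the threshold pattern 1:1:0.3 the two simulations differ in direction (33% vs 29% for the marker flag; 33% vs 38% for any of the ten tests), so no claim is made there about the flag.

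It is also fair that the error is conservative, that an empty tertile almost never occurs under the null, and that Section 12.3.3 prints case counts beside the hazard ratios, so a reader would see the zero. None of this makes the printed p-value and interval right.

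**Conclusion.** The concern holds for two reported outputs. At 25 cases the unadjusted tertile p-value is about 3% in size at nominal 5%, with a stand-alone power loss of roughly 4 to 13 points for graded effects and more for a threshold pattern. With an empty tertile the plan as written yields p = 0 and a meaningless interval. The second result rests on the robust or design-based variance, which is what the plan uses. The power figures rest on assumed effects, since the SAP states none.

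A reader might infer more, and the documents do not support it:
- That real correlates go unflagged. The resampled FWER and q-values, pooled with the quantitative tests, leave the marker flag little changed for graded effects.
- That false positives are inflated. The test errs in the conservative direction.
- That the p-value runs against the evidence. For 12/9/4, 13/9/3, 14/9/2, 15/9/1 and 16/9/0 it falls steadily: 0.169, 0.074, 0.034, 0.024, 0.
- That infinite E-values arise at 25 cases. Section 15.1.1 belongs to Controlled VE, which Tables 4 and 10 hold until 50 cases. An empty tertile is rare there except for extreme gradients.

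**What to change.** Amend Sections 12.3.3 and 12.4.2 in two respects.

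1. Take the unadjusted p-value of each of the ten tests from that test's own distribution over the 10^4 null replicates already planned, and feed those p-values into the FWER and q-value steps. Ranking each replicate's statistic among the replicates supplies the null p-values, so no second layer of resampling is needed. This is preferable to simply substituting the score test, given its 5.8% null rejection rate in the weighted simulation.
2. When any tertile has fewer than 3 cases, replace the Wald hazard ratio, p-value and interval with those from a Firth-penalised weighted Cox fit or an exact conditional method. If the sparse tertile is the Lower (reference) category, this applies to both ratios. Base any upper-limit E-value in Section 15.1.1 on that interval.

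Section 12.4.2 generally confines p-values to pre-specified, automated analyses, so the rule should be written before case status is unblinded. The cost is SAP wording and a small code change, with no new data.

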## 12.4.3 [With Day 29 markers]

If Day 29 markers are included, the same multiplicity adjustment approach is used as for Day 57 markers. The multiplicity adjustment is done separately

for Day 29 markers and for Day 57 markers, given the high degree of correlation of the analysis results (given that all endpoint cases starting 7 days post Day 57 are common among the two analyses).

## 12.5 Univariate CoR: evaluating markers as endpoints

## 12.5.1 Objective

Follmann (2018) describe a method for comparing two endpoints in terms of the sample size required to power a future study. In this approach, we imagine that our goal is to compare two (or more) markers in terms of their standardized effect size. Markers with stronger correlates signals will have higher standardized effect sizes. We then present the comparison of effect sizes in terms of a sample size ratio. For example, if the ratio of standardized effect size for Day 57 binding Ab to Spike compared to Day 57 pseudovirus neutralization ID50 is 2, then a future correlates study would need to enroll twice as many participants to achieve a similar power to reject the correlates null hypothesis for the inferior marker. The method provides, in essence, a more interpretable means of comparing the magnitude of p-values for different markers.

## 12.5.2 Approach

We will apply the approach to the univariate Cox models. The required output for the method of Follmann (2018) is the same as for the IPWCC Cox regression described above. For each marker, the Wald statistic for the associated log hazard ratio is divided by the square root of the harmonic mean of cases and non-cases in the phase 2 dataset to obtain the standardized association. Denote by  $\hat{\Delta}_m$  the standardized association for the *m*-th marker. We define the comparison of the  $\ell$ -th and *m*-th marker's standardized association to be  $\hat{\omega}_{\ell,m} = \hat{\Delta}_{\ell}/\hat{\Delta}_m$ . This is mapped into an estimated ratio of sample sizes

 $\theta_{\ell,m}$  via the following relationship

$$\hat{\theta}_{\ell,m} = \begin{cases} \hat{\omega}_{\ell,m}^2 & \text{if } \hat{\Delta}_{\ell} < 0 \text{ and } \hat{\Delta}_m < 0\\ 0 & \text{if } \hat{\Delta}_{\ell} > 0 \text{ and } \hat{\Delta}_m < 0\\ \text{undefined } \text{if } \hat{\Delta}_{\ell} > 0 \text{ and } \hat{\Delta}_m > 0\\ \infty & \text{if } \hat{\Delta}_{\ell} < 0 \text{ and } \hat{\Delta}_m > 0 \end{cases}$$

A 95% confidence interval for  $\theta_{\ell,m}$  can derived based on the bootstrap, though some cared is needed to handle edge cases. Follmann (2018) describe the following approach. For the *b*-th bootstrap sample (generated, as described above), we compute  $\hat{\Delta}_{\ell}^{(b)}$ ,  $\hat{\Delta}_{m}^{(b)}$ , and  $\hat{\omega}_{\ell,m}^{(b)}$  as described above. We then define separate "versions" of  $\hat{\theta}_{\ell,m}^{(b)}$ ,

$$\hat{\theta}_{\ell,m}^{(b)}(L) = I(\hat{\Delta}_{\ell} < 0, \hat{\Delta}_{m} < 0)(\hat{\omega}_{\ell,m}^{(b)})^{2} + I(\hat{\Delta}_{\ell} < 0, \hat{\Delta}_{m} > 0) \times \infty$$
$$\hat{\theta}_{\ell,m}^{(b)}(U) = I(\hat{\Delta}_{\ell} < 0, \hat{\Delta}_{m} < 0)(\hat{\omega}_{\ell,m}^{(b)})^{2} + I(\hat{\Delta}_{\ell} > 0, \hat{\Delta}_{m} > 0) \times \infty$$
$$+ I(\hat{\Delta}_{\ell} < 0, \hat{\Delta}_{m} > 0) \times \infty$$

The lower bound of the bootstrap 95% confidence interval is the 2.5-th percentile of the bootstrap distribution of  $\hat{\theta}_{\ell,m}^{(b)}(L)$ ; the upper bound of the bootstrap 95% confidence interval is the 97.5-th percentile of the bootstrap distribution of  $\hat{\theta}_{\ell,m}^{(b)}(U)$ .

We will compare ratios of sample sizes of the following markers:

- 1. binding Ab RBD vs. pseudovirus neutralization ID50
- 2. binding Ab RBD vs. live virus neutralization MN50
- 3. pseudovirus neutralization ID50 vs. live virus neutralization MN50

